### **Randomization**

Randomization will be used to avoid bias in the assignment of subjects to treatment, to increase the likelihood that known and unknown subject attributes (e.g., demographics and baseline characteristics) are evenly balanced across treatment groups, and to enhance the validity of statistical comparisons across treatment groups. Blinded treatment will be used to reduce potential bias during data collection and evaluation of clinical endpoints.

At the time of Screening (Visit 1A), subjects will be assigned a three-digit subject number, in ascending sequential order beginning with 001. The subject number will be retained by the subject for the duration of the study. The MGH IDS Pharmacy will provide and maintain randomization and blinding. Subjects will be randomized to receive either topiramate or placebo in a 1:1 ratio. The randomization will be balanced by using permuted blocks of 4. Subject and investigator will be blinded to treatment assignment. Subjects will be randomized sequentially as they qualify for the study.

### **Blinding**

The randomization code will be maintained by the MGH IDS Pharmacy and will not be revealed to study subjects, investigators or clinical staff until all subjects have completed and the database has been finalized.

To maintain the blind, sealed envelopes containing the study drug identification (e.g., active or placebo) will be provided to the investigator. These sealed envelopes will be kept together, in a limited access area that is accessible 24 hours per day. The study drugs will be identical in appearance and will be packaged in identical containers.

Under normal circumstances, the blind should not be broken. The blind should be broken only if specific treatment would be dictated by knowing the treatment status of the subject. Individual code breaks by the investigator will normally result in withdrawal of the subject from the trial. The date, time and reason for the unblinding must be documented in the study files.

***After the termination of the double-blind portion of the study, subjects can be made aware of the study medication they were given at their request.***

### **Medication Side Effects**

The package insert for Topamax includes warnings and precautions related to the following side effects or adverse events: acute myopia and secondary angle closure glaucoma, oligohidrosis, psychomotor slowing, difficulty with concentration, speech or language problems (word-finding difficulties in particular), somnolence, fatigue, kidney stones, paresthesia, dizziness, ataxia, difficulty with memory, and diplopia. Dose-related adverse events at doses greater than 200mg per day also include nervousness, confusion, depression, anxiety, anorexia, and weight loss.

## **STUDY EVALUATIONS**

### **General Considerations**

Starting at Visit 1, subjects will be required to keep a daily sleep and eating diary for the duration of the study. The following information will be collected: bedtime, time to fall asleep, whether the subject awoke during the night to eat, number of times the subject awoke to eat, duration and level of consciousness of each awakening, whether the subject remembers all of his/her night eating episodes, final wake time and time spent asleep. The diary will also capture the number of tablets of study medication taken. In addition, the diary includes an optional section for a bed partner or family member to provide information about witnessed night eating events.

Assessment scales included in this protocol will be administered/completed as outlined in the visit schedule. Evaluations for each phase of the study will be performed as described below.

Once a subject is randomized and is taking the study drug capsules, all visits must occur within a window of +/- 3 days of the schedule as given below.

### **Pre-randomization Phase**

The Pre-randomization Phase may last up to 42 days based on washout requirements, not including a 14-day prospective baseline period. At Visit 1A (up to Day -42), the study will be explained and subjects will provide informed consent to participate in the study. Subjects will complete Visit 1 (Day -14) screening procedures following appropriate washout of prohibited medications.

#### Visit 1A\* (Up to Day -56)

1. Obtain informed consent
2. Review inclusion/exclusion criteria
3. Assess previous and concomitant medications. Medication used for the past 42 days must be obtained.
4. Obtain detailed medical and psychiatric history and permission to contact primary care provider(s) for medical records
5. Perform physical examination
6. Perform neurological examination
7. Administer the eating disorders portion of the SCID
8. Obtain height and weight
9. Administer Hamilton Rating Scale for Depression (HAM-D)
10. Administer the Eating Attitudes Test
11. Schedule return visit

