### **Exclusion Criteria**

Subjects will be excluded from the study if they meet any of the following criteria:

1. Subjects with evidence of untreated primary sleep disorders (e.g., Obstructive Sleep Apnea, Restless Legs Syndrome, Periodic Leg Movements of Sleep) as determined in the sleep screening questionnaire and clinical history.
2. Subjects who have a DSM-IV diagnosis of substance dependence or abuse (with the exception of nicotine) that has been active within the past 6 months.
3. Subjects taking exclusionary medications, such as benzodiazepines/benzodiazepine receptor agonists, tricyclic antidepressant medications or antipsychotics as these medications have been reported to cause SRED, who are unable or unwilling to complete the required washout of these medications.
4. Subjects with an active or unstable major psychiatric disorder requiring further treatment (e.g., major depressive disorder). Subjects with clinically significant depression defined by a HAM-D >20 or who, in the investigator's judgment might require intervention with either pharmacological or non-pharmacological therapy over the course of the study, will also be excluded.
5. Subjects with an active daytime DSM-IV-TR™ diagnosis of Anorexia Nervosa or Bulimia Nervosa within the 3 months prior to screening.
6. Subjects judged clinically to be at serious suicidal or homicidal risk.
7. Subjects with a body mass index (BMI)  $\geq 50$  kg/m^2.
8. Subjects who have positive urine drug screening (phencyclidine, cocaine, amphetamines, tetrahydrocannabinol, and opiates) at Visit 1 (Day -14).
9. Subjects who report consumption of more than 2 alcoholic beverages daily, 14 or more alcoholic beverages weekly
10. Subjects who report consumption of more than 4 beverages containing caffeine daily.

11. Subjects who are rotating or third shift workers.
12. Subjects who are pregnant or lactating.
13. Subjects with a history of recurrent nephrolithiasis or on another carbonic anhydrase inhibitor.
14. Subjects with progressive or degenerative neurological disorders or a structural disorder of the brain from birth, trauma or past infection.
15. Subjects who have recently had or are planning to have surgery.
16. Subjects who have previously been treated with topiramate and discontinued treatment due to an adverse event or subjects with a known hypersensitivity to topiramate.
17. Subjects who have previously taken Topiramate.
  

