### **CONCOMITANT THERAPY**

#### **General**

Subjects may have concurrent illnesses that require prescription or over-the-counter medication during the course of the study. All exclusionary medications taken within 4 weeks (28 days) prior to Visit 1 (Day-14), with the exception of flurazepam and protriptyline which should be recorded within 5 weeks (35 days) and 6 weeks (42 days), respectively, of Visit 1, as well as those continued at the start of the study or started during the study (other than study medication), including the drug name, dose, duration and indication for use, should be recorded in the subjects' study files.

If the patient is taking a prohibited medication, the investigator and patient will discuss the risk and benefits of a trial of tapering and discontinuation of the medication. Any potential medication discontinuation will also be discussed with the prescribing physician.

Modifications to a subject's pre-existing treatment and regimen are not to be made for the explicit purpose of entering this trial, but should be done only where deemed clinically appropriate by the investigator.

The following medications are prohibited during the trial and subjects must observe the designated washout periods prior to Visit 1 (Day -14):

Prohibited Medications Prior to Visit 1 (Day –14) and During the Trial	Washout Period
Anorexic agents for obesity management, including, but not limited to: 
 
• Sibutramine (Meridia®)
 
• Orlistat (Alli™, Xenical®)
 
• Over-the-counter agents such as phentermine, hypericum
 
• Herbal preparations, including but not limited to:
 
• Mah Wang
 
• Ephedra
 
• Herbal-life
 
• Tahitian Noni-Juice
 
	4 weeks
Tricyclic Antidepressants 
 
• imipramine (Tofranil®)
 
• reboxetine (Edronax®)
 
• trimipramine (Surmontil®)
 
	1 week

 
• desipramine (Norpramine®)
 
• amoxapine (Asendin®)
 
• maprotiline
 
• nortriptyline (Pamelor®, Aventyl®)
 
• clomipramine (Anafranil®)
 
• amitriptyline (Elavil®)
 
• doxepin (Sinequan®)
 
	2 weeks

 
• protriptyline (Vivactil®)
 
	6 weeks

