### **Efficacy Analyses**

The efficacy analyses will be performed on an intent-to-treat (ITT) population defined as all randomized subjects who were dispensed study medication and for whom one post-baseline efficacy measurement is available.

Efficacy analyses will be conducted separately for subjects with night eating syndrome or sleep-related eating disorder, and across all subjects with either of these two diagnoses. The primary efficacy parameter will be the change in the number of nights per week of the specified nocturnal eating episode.

The primary efficacy parameter of number of nights per week with nocturnal episodes will be analyzed using ANCOVA with baseline frequency of nocturnal episodes as a co-variate. Diagnostic procedures will be conducted to determine whether the statistical assumptions are met.

The MOS, SDS, TFEQ, HAM-D, HbA1C, body weight and Epworth Sleepiness Scale will be analyzed using an ANCOVA with the baseline value as a covariate.

Information obtained from the sleep diaries will be summarized.

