### TIME AND EVENTS SCHEDULE

	Visit 1A (Day -56)	Visit 1 (Day -14)	Visit 2 (Day 1)	Visit 3 (Day 7)	Phone Contact (Day 14)	Visit 4 (Day 21)	Phone Contact (Day 28)	Visit 5 (Day 35)	Phone Contact (Day 42)	Visit 6 (Day 49)	Phone Contact (Day 56)	Visit 7 (Day 63)	Phone Contact (Day 77)	Visit 8 (Day 91)	Visit 9 (Day 105)
Informed Consent	X														
Review Inclusion/Exclusion Criteria	X	X	X												
Concomitant Medication Review	X	X	X	X	X	X	X	X	X	X	X	X	x	X	X
Medical & Psychiatric History	X														
Physical Examination	X														
Neurologic Examination	X														
SCID Eating Disorders	X														
Weight	X	X	X	X		X		X		X		X		X	X
Urine Pregnancy Test		X						X				X			
Urine Drug Screen		X													
Blood HbA1C		X*												X	
MOS			X					X				X		X	
Epworth Sleepiness Scale			X					X				X		X	
HAM-D	X							X				X		X	
TFEQ		X												X	
EAT	X														
Sheehan Disability Scale		X												x	
Dispense Sleep and Night- Eating Diary		X	X	X		X		X		X		X			
Review Sleep and Night- Eating Diary			X	X	X	X	X	X	x	X	x	X	X	X	
Record Adverse Events		X	X	X	X	X	X	X	X	X	X	X	X	X	X
Dispense Study Medication			X	X	X	X	X	X	x	X	x	X	x	X	
Collect study medication and perform drug accountability				x		x		X		X		X		x	X

\*Creatinine also tested at visit 1

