**Part III:**

51. On a scale of 1 to 6, where 1 means no restraint in eating (eat whatever you want, whenever you want it) and 6 means total restraint (constantly limiting food intake and never “giving in”), what number would you give yourself?

1. eat whatever you want, whenever you want it
2. usually eat whatever you want, whenever you want it
3. often eat whatever you want, whenever you want it
4. often limit food intake, but often “give in”
5. usually limit food intake, rarely “give in”
6. constantly limiting food intake, never “giving in”

[figure not shown]

**Attachment 6:  
Sheehan Disability Scale (SDS)**

Instructions: Please mark ONE box for each scale based on your symptoms over the past week.

[figure not shown]

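### In subjects who undergo psychotropic washout, the only pre-randomization HAM-D precedes washout, so the HAM-D >20 exclusion is not re-checked by score and the HAM-D covariate may be an on-drug value 3 to 8 weeks old

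*Combined protocol and SAP*

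**What the plan says.** The Visit 1A procedure list includes "Administer Hamilton Rating Scale for Depression (HAM-D". The Visit 1 and Visit 2 lists do not include the scale. The Time and Events Schedule agrees: the HAM-D row has a single pre-randomization mark, in the column headed "Visit 1A (Day -56"). The next HAM-D is at Visit 5 (Day 35).

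Exclusion criterion 4 sets a numeric limit: "Subjects with clinically significant depression defined by a HAM-D >20". It adds a limb that rests on the investigator's judgment and needs no score. The Double-Blind Phase section randomizes at Visit 2 only those who still satisfy every entry criterion.

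On the order of events, the Pre-randomization Phase section states: "Subjects will complete Visit 1 (Day -14) screening procedures following appropriate washout of prohibited medications". The Concomitant Therapy section states: "The following medications are prohibited during the trial and subjects must observe the designated washout periods prior to Visit 1 (Day -14"). Its table gives washouts of 1 to 6 weeks.

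Under Efficacy Analyses, HAM-D is one of seven measures that "will be analyzed using an ANCOVA with the baseline value as a covariate". No visit is named as the baseline for any of them.

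**The concern.** The protocol applies its depression limit by score before the step most likely to move that score. Some of the drugs withdrawn are antidepressants. Others are hypnotics and benzodiazepines, whose withdrawal could plausibly shift the three HAM-D insomnia items (0 to 2 points each, so up to 6 points) and the two anxiety items. The criteria review at Visit 2 has no scheduled post-washout score to work with. The protocol also warns of mood effects of the study drug: "Dose-related adverse events at doses greater than 200mg per day also include nervousness, confusion, depression, anxiety, anorexia, and weight loss".

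The analysis inherits the same score. For a washed-out subject, the ANCOVA covariate describes a different drug state from the one in which study treatment starts. Change from that value combines the effect of stopping the earlier drug with whatever happens on study medication.

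**Working it through.** The documents give no figure to reproduce on this point: the sample size was not based on statistical considerations, and no alpha, SD or correlation is stated.

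**1. Age of the score at Day 1.** Visit 1 is at Day -14 and washout must be complete by then. For a subject still on the drug at Visit 1A, the minimum gap is the washout length plus the 14-day baseline period.

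| Washout | Examples from the Concomitant Therapy table | Minimum gap to Day 1 |
|---|---|---|
| 1 week | imipramine, lorazepam | 7 + 14 = 21 days |
| 2 weeks | most other tricyclics, mirtazapine, zolpidem | 14 + 14 = 28 days |
| 3 weeks | clonazepam, haloperidol | 21 + 14 = 35 days |
| 4 weeks | phenelzine, olanzapine | 28 + 14 = 42 days |
| 5 weeks | tranylcypromine, flurazepam | 35 + 14 = 49 days |
| 6 weeks | protriptyline | 42 + 14 = 56 days |

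The gap is thus 3 to 8 weeks. The upper end uses Day -56 for Visit 1A, as in the visit heading and the schedule table. The Pre-randomization Phase text says Day -42, which would leave only 28 days before Visit 1 and could not hold a 5- or 6-week washout begun at Visit 1A. Subjects who need no washout may combine Visits 1A and 1; their score is about two weeks old and their drug state does not change.

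**2. Could the >20 limit be crossed unseen?** This is illustration only; the starting score, mean rise and SD of change are all assumed. With a normal change, P(score > 20) = 1 - Phi((20.5 - start - rise)/SD).

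| Visit 1A score | Rise 0 (SD 3; 5) | Rise 3 (SD 3; 5) | Rise 6 (SD 3; 5) |
|---|---|---|---|
| 10 | 0%; 2% | 1%; 7% | 7%; 18% |
| 14 | 2%; 10% | 12%; 24% | 43%; 46% |
| 18 | 20%; 31% | 57%; 54% | 88%; 76% |

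The risk is negligible for low starting scores and substantial only for scores near the limit or sizeable rises.

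**3. Precision of the HAM-D ANCOVA.** Residual variance is proportional to 1 - rho², where rho is the correlation of baseline with outcome. Assume rho = 0.6 for a Day 1 score and 0.45 or 0.3 for a pre-washout score:

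- Day 1: 1 - 0.36 = 0.64.
- rho 0.45: 1 - 0.2025 = 0.80; ratio 0.80/0.64 = 1.25.
- rho 0.3: 1 - 0.09 = 0.91; ratio 0.91/0.64 = 1.42.

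These 25% to 42% increases apply only to affected subjects. If a quarter of the sample were affected (also assumed), the simple weighted average increase is 0.25 × 25% = 6% to 0.25 × 42% = 11%. As an outer bound with all 40 affected, the difference detectable with 20 per arm (two-sided 5%, 80% power, both assumed) is (1.96 + 0.84) × sqrt(1 - rho²) × sqrt(2/20). That is 0.71 SD at rho 0.6 and 0.85 SD at rho 0.3.

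**4. Bias.** Visit 1A and washout both precede random allocation. The effect of stopping earlier drugs is therefore balanced between arms in expectation, and adjusting for a pre-randomization covariate, however stale, introduces no bias.

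**The case against.** The case against giving this much weight is strong, and most of it stands.

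- **Safeguards exist.** A reader might infer that a subject who deteriorates in washout would pass unchecked into the trial. The text does not support that. Criteria are reviewed at Visits 1 and 2, adverse events are recorded at both, exclusion 4 has its judgment limb, and exclusion 6 covers suicidal or homicidal risk. The >20 limit is not tied to Visit 1A, so nothing forbids a repeat rating. What remains is that no repeat is scheduled, so the numeric part of the criterion goes unverified.
- **The dose argument is limited.** On the suggested titration, a dose above 200 mg/day is first reached on Day 50, after the Day 35 HAM-D, when the scheduled dose is 125 mg. That rating helps with monitoring, but it comes after randomization and cannot serve eligibility.
- **No confounding.** A reader might infer that washout confounds the treatment comparison. It does not, for the reason in step 4. Only within-arm change is hard to read, and no within-arm test is planned.
- **The affected group may be small.** SSRIs are not in the prohibited table. The Concomitant Therapy section also says that existing treatment is not to be changed for the explicit purpose of entering the trial.
- **The Sheehan Disability Scale does not share the problem.** It is given at Visit 1 and asks the subject: "Please mark ONE box for each scale based on your symptoms over the past week". Because the shortest washout is one week and must be complete by Visit 1, that week is already off the drug.

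**Conclusion.** The point holds for subjects who are on a prohibited psychotropic at Visit 1A and then stop it. For them the only pre-randomization HAM-D is an on-drug score taken 3 to 8 weeks before Day 1. The existing >20 exclusion cannot be verified by score when they are randomized; clinical judgment covers this in part. The timing follows directly from the visit lists, the schedule table and the washout table.

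The analytic cost is modest. The between-arm ANCOVA is unbiased. The precision loss cannot be computed from the documents, and the figures above rest on assumed correlations and an assumed affected share. HAM-D is a secondary measure, and the primary diary baseline is collected over the 14 days after washout. This is a cheap improvement that should be made, not a defect that undermines the trial.

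**What to change.** Add HAM-D to the Visit 2 (Day 1) list and to the Visit 2 column of the Time and Events Schedule, to be scored before randomization. Subjects who underwent washout are the minimum; rating everyone would give all subjects a baseline at the same time point. Apply the existing HAM-D >20 criterion to that score. In Efficacy Analyses, state that the HAM-D baseline is the last score before randomization.

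While editing, reconcile the Day -42 and Day -56 timings for Visit 1A. Also reconcile the Visit 7 HAM-D, which is marked in the schedule table but absent from the Visit 7 list.

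The cost is one extra 17-item rating by existing staff at an existing visit, and possibly a few subjects who fail screening after completing washout and the diary baseline. No change to the Sheehan Disability Scale is needed.

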#### Visit 1\* (Day -14)

1. Review inclusion/exclusion criteria
2. Assess concomitant medications
3. Obtain weight
4. Obtain non-fasting clinical laboratory tests as follows:
  - Urine Drug Screen [cocaine, amphetamines, methamphetamines, benzodiazepines, tetrahydrocannabinol (THC), and opiates].
  - Hemoglobin A1C
  - Creatinine (creatinine clearance will be calculated using standard formula)
5. Perform urine pregnancy test (subjects of childbearing potential only)
6. Administer the Three Factor Eating Questionnaire (TFEQ)
7. Administer the Sheehan Disability Scale
8. Dispense sleep and night eating diary
9. Record adverse events
10. Schedule return visit

\*Visits 1A and 1 may be combined for subjects who do not require washout from prohibited medications.

Subjects who are eligible for study entry based on the results of the above will be instructed to return for Visit 2 (Day 1).

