#### Visit 5 (Day 35)

1. Assess concomitant medications
2. Obtain weight
3. Perform urine pregnancy test (subjects of childbearing potential only)
4. Administer the Medical Outcome Study (MOS) Sleep Scale
5. Administer the Epworth Sleepiness Scale
6. Administer the HAM-D
7. Collect and review sleep and night eating diary
8. Dispense sleep and night eating diary
9. Collect study medication and perform drug accountability
10. Record adverse events
11. Dispense study medication
12. Schedule phone contact in one week and return visit in two weeks

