#### Visit 7 (Day 63)

1. Assess concomitant medications
2. Obtain vital signs (sitting blood pressure, pulse, and weight)
3. Perform urine pregnancy test (subjects of childbearing potential only)
4. Administer the Medical Outcome Study (MOS) Sleep Scale
5. Administer the Epworth Sleepiness Scale
6. Collect and review sleep and night eating diary
7. Dispense sleep and night eating diary
8. Collect study medication and perform drug accountability
9. Record adverse events
10. Dispense study medication
11. Schedule return visit in four weeks

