#### Visit 8 (Day 91)

1. Assess concomitant medications
2. Perform physical examination
3. Obtain weight
4. Administer the Medical Outcome Study (MOS) Sleep Scale
5. Administer the Epworth Sleepiness Scale
6. Administer the HAM-D
7. Administer the TFEQ

8. Administer the SDS
9. Obtain blood sample for HbA1C
10. Collect and review sleep and night eating diary
11. Collect study medication and perform drug accountability
12. Record adverse events
13. Dispense medication and instruct the subject on tapering.
14. Schedule Post-Taper Visit 9 (Day 105) in approximately 2 weeks

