#### **Clinical Laboratory Tests**

Laboratory data will be summarized by treatment group by the type of laboratory test.

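### Creatinine is measured only before randomization, and blood pressure and pulse only at Day 63, so the safety summaries can show no change from baseline in any of them

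*Combined protocol and SAP*

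**What the plan says.** The Objective section names efficacy and safety together. Under Safety Analyses, the laboratory plan is one sentence: "Laboratory data will be summarized by treatment group by the type of laboratory test". It does not name the tests or time points. No analysis of vital signs is described.

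The assessments behind that plan are as follows.

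- **Creatinine.** Visit 1 (Day -14), item 4: "Creatinine (creatinine clearance will be calculated using standard formula". The footnote to the Time and Events Schedule agrees: "Creatinine also tested at visit 1". No other visit lists it.
- **HbA1C.** Taken at Visit 1 and again at Visit 8 (Day 91): "Obtain blood sample for HbA1C". The Efficacy Analyses section claims it: "The MOS, SDS, TFEQ, HAM-D, HbA1C, body weight and Epworth Sleepiness Scale will be analyzed using an ANCOVA with the baseline value as a covariate".
- **Blood pressure and pulse.** Visit 7 (Day 63) only: "Obtain vital signs (sitting blood pressure, pulse, and weight". The Time and Events Schedule has a weight row but none for blood pressure or pulse.
- **Neurological examination.** Visit 1A only: "Perform neurological examination".
- **Physical examination.** The Visit 8 list includes one. The Time and Events Schedule marks it only at Visit 1A.

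**The concern.** A by-group safety summary tells the reader something about the drug only if it contains values taken after dosing began. Creatinine has none. Its table would show two randomized groups two weeks before treatment, where any difference is chance.

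Creatinine is not a peripheral test in this protocol. The Pharmacokinetic Profile names the kidney as the main route of elimination, the exclusion criteria include a creatinine clearance limit, and a footnote to the titration schedule assigns a modified schedule by clearance. A reader of the final report would expect to see creatinine by arm at the end of treatment, and the plan cannot supply it.

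Blood pressure and pulse have the opposite gap: one on-treatment reading and no listed baseline. What is at stake is the descriptive value of the safety results, which are part of the primary objective and come from only 40 planned randomized subjects.

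**Working it through.** The plan states no figure to reproduce. The check is a count of scheduled assessments, using the visit lists from Visit 1A to Visit 9, the Early Withdrawal section and the Time and Events Schedule.

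| Assessment | Before dosing | On treatment | Change from baseline possible? |
|---|---|---|---|
| Creatinine | 1 (Visit 1) | 0 | No |
| Urine drug screen | 1 (Visit 1) | 0 | No |
| HbA1C | 1 (Visit 1) | 1 (Day 91) | Yes, analysed as efficacy |
| Blood pressure and pulse | 0 | 1 (Day 63) | No |
| Neurological examination | 1 (Visit 1A) | 0 | No |
| Urine pregnancy test | 1 (Visit 1) | 2 (Days 35 and 63) | Not applicable |

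The pregnancy test ("Perform urine pregnancy test (subjects of childbearing potential only" at Visit 5) serves safety, but Visit 1 lists it as an item separate from the clinical laboratory tests. Of the three clinical laboratory tests at Visit 1 (drug screen, HbA1C, creatinine), one is repeated on treatment, and no renal or other safety chemistry is.

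**Age of the only creatinine value.** Assume there is no Day 0, since the schedule passes from negative days to Day 1.

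- At the end of maintenance: 91 + 14 - 1 = 104 days.
- At the post-taper visit: 105 + 14 - 1 = 118 days.

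**Vital signs.** Day 63 falls on treatment, 91 - 63 = 28 days before Visit 8. With 1:1 randomization of 40 subjects, about 40 / 2 = 20 per arm could be compared at that visit, fewer after dropout. That comparison is valid because the arms are randomized, but it has no baseline to adjust for. The precision lost depends on the correlation between baseline and Day 63 readings, which the documents do not give.

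**Early withdrawals.** The Early Withdrawal section sends these subjects to the Visit 8 procedures. As listed, those include no creatinine, blood pressure, pulse or neurological examination, so subjects who leave because of adverse events also have no end-of-treatment value.

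**The case against.** The strongest reply is that this is a single-center pilot of a marketed drug, with renal exclusions at entry, and that its main safety instrument is adverse event recording. Events are recorded at every visit and telephone contact from Visit 1 to Visit 9 and tabulated by group, and the definition of an event covers abnormal examination and laboratory findings. On this view, how much routine testing to add is a matter of preference. The laboratory sentence also does not promise on-treatment chemistry or change from baseline, so it is thin rather than contradictory.

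Much of that stands, and it rules out several stronger readings that a reader might infer:

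- *That none of these measures can show a drug effect.* This is too strong for blood pressure and pulse, because the Day 63 readings can be compared with placebo. Only change from baseline is lost.
- *That the laboratory summary would hold no on-treatment data.* Day 91 HbA1C can appear there; its efficacy ANCOVA does not bar it.
- *That the neurological risks go unmeasured.* Many of those named under Medication Side Effects are symptoms a subject can report. The HAM-D, listed at Visits 1A, 5 and 8, has an item on slowed thought and speech and impaired concentration. The Epworth scale covers sleepiness on Days 1, 35, 63 and 91. The examination itself is not repeated, but that is a smaller gap.
- *That a fall in clearance past the protocol's limits would be missed.* The limits of 60 and 70 are entry and titration criteria. The documents state no on-treatment threshold, and a Day 91 value would come too late to act on for those who complete.
- *That the drug is expected to impair renal function.* The documents say the kidney clears the drug, and they name kidney stones as a risk. They do not say that it lowers clearance or that creatinine detects stones.

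What the reply does not answer is the between-arm description. Tests prompted by an event are not systematic across arms, and a change in creatinine without symptoms would not be reported by the subject.

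**Conclusion.** The point holds as a gap in what the safety summary can show. The schedule yields no on-treatment creatinine value, so the arms can be compared on creatinine only before randomization. Blood pressure and pulse permit one between-arm comparison, at Day 63, and no change from baseline. HbA1C is the only clinical laboratory test repeated on treatment, and it is assigned to efficacy. The mismatch over the Visit 8 physical examination is a separate clerical discrepancy.

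This is a modest, inexpensive improvement and not a flaw that invalidates the trial. It does not show that subjects are unprotected during treatment. The conclusion assumes that the visit lists are complete. The content of the physical examinations is not defined, so they may include blood pressure or neurological signs that are not listed. Unscheduled tests remain possible but would not give comparable data by arm.

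**What to change.** 1. Measure creatinine, with calculated clearance, at the blood draw already planned for Visit 8. Under Clinical Laboratory Tests, name the tests and state that creatinine change from Visit 1 will be summarized by treatment group.
2. Take sitting blood pressure and pulse at Visit 2, before the first dose, and at Visit 8, to pair with Day 63. Add a row for them to the Time and Events Schedule and a sentence under Safety Analyses: values and change from Visit 2, by group.
3. Reconcile the Visit 8 list and the Time and Events Schedule on the physical examination. Repeating the neurological examination at the same visit is optional, and the point does not depend on it.

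Because early withdrawals are sent to Visit 8 procedures, the Visit 8 additions reach them too. Label these values as end of treatment, since their timing will vary.

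The cost is one extra assay and a few minutes at existing visits, with no new visit. The documents do not describe the HbA1C sample, so a second tube at the same draw may be needed. The Visit 8 creatinine serves the between-arm safety comparison only; it does not act as monitoring during treatment, and no clinical limit is proposed here.
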